**Definitions:**

The *diagnosis criteria for PVC-CM* is based on LVEF  $\leq$  45% (by echocardiography) and average PVC burden  $\geq$  10% in an ambulatory ECG Holter monitor that meet the inclusion and exclusion criteria (Table 1), regardless of severity and time of onset. LVEF and PVC burden must be within 150 days of Enrollment Visit (Day 0).

*Responders are defined as an LVEF increase greater than 10% points regardless of intervention.*

If screening confirms eligibility (LVEF  $\leq$ 45% and PVC burden  $\geq$  10%), a baseline visit will be scheduled to obtain subject's demographics and medical history, 12-lead ECG, Minnesota living with HF quality of life (QOL) questionnaire, NYHA functional class and cardiac magnetic resonance (CMR) if clinically indicated. Subjects that refuse enrollment, will be asked to participate in a PVC-CM registry to follow their response and crossover to different treatment strategies.

If subjects meet inclusion criteria (Table 1) during screening, informed consent should be obtained. Stratified randomization to either RFA or AADs will be performed at the time of enrollment (baseline visit, week 0). Based on our preliminary data, we expect that around 30% of subjects will have a PVC burden  $>$ 20%. Thus, a *stratified randomization based PVC burden (assessed by Holter) above and below 20% is needed to assure that subjects in both groups (RFA vs. AAD) are equally distributed between PVC burden above and below 20%.* Stratified randomization will be performed using approved software available at the Coordinating Center only.

If a subject is randomized to the RFA arm, a RFA procedure (Visit 1) should be scheduled at the time of randomization due to usual 8-week next available RFA appointment in most participating centers. Yet both, RFA and AAD interventions should only occur or be initiated after completion of a 3-month observation (Table 2 - Visit Tx-V1, week 12-15).

A 3-month observation period will assess spontaneous variation of PVC burden and improvement or deterioration of LV function. During the final 3-month observation visit (Week 12), LVEF and Holter will be repeated to confirm eligibility if PVC burden and LVEF remains  $\geq$ 10% and  $\leq$ 45%, respectively.

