**Table 2. Table of Study Procedures**

	3-month Observation			12-month Treatment Phase					
	Obs-V1 Baseline	Obs-V2 2-mo	Obs-V3 3-mo	Tx-V1 Baseline	Tx-V2 1-mo	Tx-V3 3-mo	Tx-V4 6mo	Tx-V5 9-mo*	Tx-V6 12-mo
Timeline in Weeks (range of days)	Week 0 (Day 0)	Week 9 (51-63)	Week 12 (84-96)	Week 12-15 (84-105)	Week 21 (141-153)	Week 26 (176-188)	Week 38 (260-272)	Week 50 (344-356)	Week 64 (441-454)
Informed consent	X								
Inclusion/Exclusion Criteria	X								
Collection of demographic data	X								
Medical History	X								
Physical Exam	X		X		X	X	X	X	X
Functional status/NYHA class	X		X		X	X	X	X	X
QOL Minnesota HF Questionnaire	X		X		X	X	X	X	X
Current / change of medications	X		X		X	X	X	X	X
12-lead ECG	X*	X*	X		X*	X*	X*	X*	X*
Ziopatch	X	X ‡			X €	X	X		X
Echo	X £		X ‡			X	X*		X
BNP / ProBNP levels ESR & CRP	X* £		X*		X*	X*	X*	X*	X*
Urine pregnancy test (if applicable)	X		X	X	X	X	X	X	X
CMR	X*								
TSH (if assigned to amiodarone)			X				X		X
LFT (AST) (if assigned to amiodarone)			X				X		X
Treatment randomization	X								
Initiation of RFA or ADD				X					

Collection of unsolicited AEs	From Obs-Visit 1 until Tx-Visit 6
--------------------------------------	-----------------------------------

Footnote: \*, visit/intervention if clinically indicated.

‡ LVEF results of 2D-echocardiogram and Ziopatch have to be available at the time of Observation Visit 3 (Obs-V3). € If PVC burden >10%, subject should be considered to either adjust antiarrhythmic therapy (AAD group) or second ablation procedure (RFA group) based on their randomization group. ESR, Erythrocyte sedimentation rate; CRP, C-reactive protein. £ Must be done within 150 days of Enrollment Visit (Day 0)

Crossover between PVC suppression strategies is not encouraged. We request that crossover only be considered after 6 months of initiation of treatment, for which an intention-to-treat analysis will be performed. However, if crossover occurs before 6 months of initiation of treatment, subjects will be withdrawn from the study and included in the PVC-CM registry if the subject provided consent.

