v. *Treatment – Visit 2.* Using appropriate data collection forms, we will ask that sites obtain current medical therapy information, NYHA functional class and Minnesota HF quality of life questionnaire (QOL). 12-lead ECG should be obtained if clinically indicated. A repeat Zio Patch should be placed to re-assess adequate PVC suppression after RFA or initiation of AADs. The local PI and designated site staff will be able to log in to iRhythm’s ZioReports) 3 weeks later to obtain a Zio Patch Report with repeat PVC burden after intervention. If PVC burden is suppressed by more than 80%, intervention is considered successful and the subject should continue with treatment visits as scheduled,

However, if PVC burden does not decrease by more than 80%, intervention is considered a failure. In such a case, the subject should be considered for a second RFA procedure or a different antiarrhythmic drug depending on the randomization group that the subject was assigned (see Section C: Description of the Intervention/treatment). We discourage crossover of treatment arms since this will result in automatic withdrawal from the study. Nevertheless, subjects that withdraw from the study will be included in a PVC-CM registry if the subject provided consent. (described above Section A.1).

**Figure 1.** PAPS study design. A 3-month Observation (Obs) period allows each subject to serve as their own control to assess benefits of PVC suppression. All subjects will be randomized (R) to either RFA or AADs. OMT, optimal medical therapy. QOL, quality of life questionnaire; NYHA, New York Heart Association class; LVEF, LV ejection fraction; Zio, ambulatory ECG Ziopatch Holter, CMR, Cardiac MRI (\*, visit/intervention if clinically indicated).

vi. *Treatment – Visit 3.* Appropriate data collection forms should be used to collect current medical therapy information, NYHA functional class and Minnesota HF quality of life questionnaire (QOL). 12-lead ECG should be obtained if clinically indicated. A transthoracic echocardiogram should be performed to assess LVEF and a copy mailed to the Echo Core laboratory led by [name] III, M.D. A repeat Zio Patch should be placed to re-assess PVC burden. Local PI and designated site staff will be able to log in to iRhythm’s ZioReports 3 weeks later to obtain a Zio Patch Report if desired for any clinical decision.

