#### **D. Description of the intervention(s)/treatment(s).**

Prior to intervention, all subjects should complete a 3-month observation period consisting of a total of 3 visits. Subjects that are not able to wait or be observed for this period of time should not be considered for this study. Subjects will be randomized to intervention at the baseline visit of observation. Crossover between different treatment arms (RFA vs. AADs) is not encouraged and will not be allowed before 6-month follow-up duration of the treatment period, unless considered critical for the subject's well-being.

ii) Treatment or intervention arms will consist of: Antiarrhythmic drug (AAD) therapy. AAD therapy of choice is amiodarone due to its proven safety in subjects with LV dysfunction. Amiodarone loading dose of 10 grams is recommended, followed by maintenance dose of 200-400mg daily to achieve successful PVC suppression. We define successful PVC suppression only if  $\geq 80\%$  absolute reduction in PVC burden is achieved after a drug or intervention. Alternatively, sotalol and/or propafenone could be considered at the discretion of the electrophysiologist (sotalol dose of at least 120mg twice daily, propafenone 150-300mg tid) if there is a significant concern of safety profile of amiodarone. Finally, other AADs (class Ic) are acceptable if there is a clear preference by the clinical electrophysiologist while a rationale is requested for such choice. Overall, we suggest avoiding class Ia antiarrhythmic drugs due to the prior documented risk of pro-arrhythmia, however, they could be considered in subjects with an implantable or external defibrillator (Lifetest). Optimal heart failure medical therapy should be continued in combination with AAD throughout the 12-month follow-up. Throughout the 12-month follow up period, subjects will have a total of 5 visits to assess changes in clinical status, arrhythmia burden including PVCs and LVEF as outlined in Table 2 and Figure 1. In addition, subjects receiving amiodarone as antiarrhythmic (AAD group) will require a baseline TSH and LFTs and should be repeated every 6 months.

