A 2-week ambulatory ECG Holter (Zio Patch, IRhythm, Inc.) will be obtained 4-6 weeks after initiation of AAD to assess whether PVC suppression was successful (defined above). If successful PVC suppression is not achieved, we will ask sites to consider either an increase in the antiarrhythmic dose or change of antiarrhythmic as noted above. A repeat 2-week ambulatory Holter monitor will be done 4 weeks after adjustment of AAD to re-assess PVC suppression.

Radiofrequency Ablation (RFA) of PVCs. RFA will be performed after completion of 3-month observation period). EPS will be performed on their baseline medications, except for antiarrhythmic drugs class II (beta blockers) which will be held at least 5 half-lives prior to procedure. Beta blockers should be resumed after RFA.

EPS and RFA will be performed using standard techniques and protocols similar to those subjects that do not participate in this clinical study. Multipolar electrode diagnostic catheters will be inserted. If no ectopy is present at baseline, isoproterenol may be infused at rates up to 10mcg/min. If the ectopy is infrequent despite adrenergic stimulation, pace mapping will be performed at a pacing cycle length determined by coupling interval of the spontaneous ventricular ectopy. RV or LV PVCs will be mapped/ablated at the discretion of the electrophysiologist. Coronary angiography and/or intracardiac echo will be performed as needed. RFA will be performed at the site of earliest endocardial activation or best pace map. RFA applications will be delivered for at least 30 seconds if adequate power at the electrode-tissue interface is achieved. RFA will be continued for at least 60-120 seconds in sites where PVCs are abolished within 30 seconds. After ablation of the PVCs, isoproterenol will be administered at 2-10 mcg/min as required to shorten sinus CL to 500ms to confirm that PVCs are not inducible by adrenergic stimulation. In the event of polymorphic PVCs, all morphologies are to be targeted for ablation. Subjects will be observed overnight in a telemetry bed and discharged home the next day, as it is current standard of care.

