During enrollment and immediately after RFA, baseline medical therapy (including ACE inhibitors/ARB, beta blockers) should be optimized or continued throughout the 12-month follow-up period. Practitioners will be asked to document any changes in medical therapy including rationale. All events, side effects as well as change or decrease of doses will be documented and rationale explained. Similar to the AAD group, subjects will have 5 follow-up visits (Visit 2 – 6, Table 2 and Figure 1) to assess changes in clinical status, arrhythmia burden including PVCs and LVEF.

A 2-week ambulatory ECG Holter (Zio Patch, IRhythm, Inc.) will be obtained 4-6 weeks after RFA to assess whether PVC suppression was successful (defined above). If successful PVC suppression is not achieved, subjects will be offered a second PVC-RFA procedure 3 months after initial randomization. Redo-RFA will be performed with a similar approach as the first intervention; however, epicardial mapping will be encouraged if considered appropriate. This subgroup of subjects will have a repeat 2-week Holter monitor within 2-4 weeks after redo-RFA to document successful or failure of PVC suppression. All events and complications in the PVC suppression arm related to RFA will be documented.

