##### ***Sampling plan, recruitment and retention strategies and criteria for inclusion or exclusion of any subpopulation.***

A signed informed consent will be obtained from each participating subject. Inclusion and exclusion criteria are the same for all subjects regardless of gender, age, race or ethnic group (See details in document: Study Design – Part I: Table 1). We plan to recruit study subjects using different strategies and settings, but primarily by: 1) Engaging clinicians and consultants to identify subjects during visits to Primary care and cardiology clinics, Device and arrhythmia clinic, Non-invasive cardiac laboratory, heart failure clinic, and hospital admissions; 2) local heart failure service, and most importantly 3) screening of ambulatory ECG Holters that will allow us to identify subjects with frequent PVCs (Design Study – Part II). Due to inaccessibility to some subjects with previous Holters, a waiver of informed consent and a waiver of HIPAA will be requested for subjects in Part II as they may not be accessible for consent.

As a retention strategy, we will request each participating center to remain engaged with active study subjects through local heart failure groups and monthly emails or phone calls.

***Procedures for assignment to a study group. As related to human subject's protection, describe and justify the selection of an intervention's dose, frequency and administration.***

This is a *prospective randomized-controlled study* of subjects with CM and high PVC burden with a likely diagnosis of PVC-CM, where individual subjects will be assigned with a 1:1 random allocation to one of two un-blinded parallel groups (Figure 1): 1) PVC radiofrequency ablation (RFA) vs. 2) AADs. Since we expect about 30% of subjects will have a PVC burden >20%, we plan a stratified randomization based on PVC burden above and below 20% reported by at least a 24-hour Holter. Stratified randomization will assure equal distribution of subjects between PVC burden above and below 20%. Stratified randomization will be performed only at the Coordinating Center using biostatistics software and/or service (randomization.net). This stratified randomization will assure that both groups (RFA vs. AADs) are equally distributed between PVC burden above and below 20%.

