A few small studies suggest that an overall PVC burden more than 20% may affect LV function and NYHA functional class. In contrast, PVC burden of less than 10% is less likely associated with impairment of LV function. Interestingly, a few studies with PVC burden as low as 10 PVCs per hour have shown some degree of improvement in LV ejection fraction after PVC suppression. Based on limited data, we chose  $\geq 10\%$  PVC burden as inclusion criteria for our study, as we believe these are subjects with a higher likelihood of a diagnosis of PVC-CM.

As proposed in this study, we have an observation period that would allow us to assess and compare no active intervention (3-month observation) vs. PVC suppression (treatment phase). Moreover, our study design will allow us to compare two PVC suppression strategies: 1) RFA versus 2) AADs. Successful PVC suppression is defined as a decrease in 80% of PVC burden after 2-4 weeks of procedure. Single RFA of PVCs has been shown to be successful in more than 80% of cases. As in current practice, we plan to repeat a second RFA after 4-6 weeks on those subjects with unsuccessful RFA (less than 80% decrease in PVC burden after RFA group). Since all subjects will start or continue optimal medical therapy regardless of treatment randomization, they will be followed approximately every 3 months in order to assure compliance and assess potential side effects.

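### The re-treatment prompt at Treatment Visit 2 has two unreconciled thresholds: residual PVC burden above 10% in the Table 2 footnote, failure to reach an 80% reduction in the text

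*Combined protocol and SAP*

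**What the plan says.** Two cut-offs are attached to the post-treatment Zio Patch at Treatment Visit 2.

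- **Table 2, footnote to that monitor:** "If PVC burden >10%, subject should be considered to either adjust antiarrhythmic therapy (AAD group) or second ablation procedure (RFA group"). The threshold is the burden that remains.
- **Section B, Treatment – Visit 2:** "However, if PVC burden does not decrease by more than 80%, intervention is considered a failure". A subject who fails should then be considered for a second ablation or a different drug, according to arm. The threshold is the size of the fall.
- **Section D, AAD arm:** if suppression is not successful, "we will ask sites to consider either an increase in the antiarrhythmic dose or change of antiarrhythmic".
- **Section D, RFA arm:** "If successful PVC suppression is not achieved, subjects will be offered a second PVC-RFA procedure".
- **Protection of Human Subjects, on assignment to a study group:** a second ablation is planned for "those subjects with unsuccessful RFA (less than 80% decrease in PVC burden after RFA group").

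Both Section D rules rely on that section's definition of success, which sets the bar at 80% and describes it as an "absolute reduction in PVC burden is achieved after a drug or intervention". No section ranks the footnote against the 80% rule or describes it as an additional prompt.

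On where subjects will lie, the Definitions in Section A state that "we expect that around 30% of subjects will have a PVC burden" above 20%. The Protection of Human Subjects section repeats this expectation.

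**The concern.** The footnote and the visit text lead to the same action on the basis of the same recording, but they select different subjects. A fixed residual of 10% is a demanding target for someone who starts at 60% and almost no target for someone who starts near the 10% entry threshold. The 80% rule scales with the starting burden; the footnote does not.

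The decision at stake is whether to repeat an invasive procedure or change an antiarrhythmic drug. Table 2 is the page a coordinator is likely to use as a visit guide, and the plan expects about three subjects per center, so sites that read it differently would add variation between centers in how treatment is delivered. Section F intends the pilot's suppression and adverse-event rates to inform the design and power of the full trial, and both rates depend in part on who is re-treated.

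**Working it through.** The plan gives no figure to reproduce here; the check is a direct comparison of the two rules.

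**Inputs**
- Footnote: flag if the residual R exceeds 10% (Table 2).
- 80% rule: success if the proportional fall from pre-treatment burden B reaches 80%, that is, R ≤ 0.2B (Sections B and D; Protection of Human Subjects). The difference between more than 80% and at least 80% matters only at exactly 80% and is set aside here.
- B is at least 10% at entry and must still be so at the end of observation (Table 1; Section B, Observation – Visit 3).
- About 30% of subjects are expected above 20% burden (Section A, Definitions), hence about 70% at or below 20%.
- Planned enrollment is 36–39.

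**Step 1. Put both rules on one scale.** A residual of 10% is a proportional fall of (B − 10)/B.

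| B (%) | Highest residual that is a success, 0.2B (%) | Footnote cut as a proportional fall | Residuals on which the rules disagree (%) |
|---|---|---|---|
| 10 | 2 | 0% | above 2, up to 10 |
| 15 | 3 | 33.3% | above 3, up to 10 |
| 20 | 4 | 50% | above 4, up to 10 |
| 30 | 6 | 66.7% | above 6, up to 10 |
| 40 | 8 | 75% | above 8, up to 10 |
| 50 | 10 | 80% | none |
| 60 | 12 | 83.3% | above 10, up to 12 (reversed) |

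**Step 2. Below B = 50%.** Here 0.2B is less than 10, so any R above 10 also exceeds 0.2B. Everyone the footnote flags has already failed the 80% rule, but not everyone who fails is flagged.
- 20% to 8%: (20 − 8)/20 = 60%, a failure in the text, not flagged.
- 15% to 9%: (15 − 9)/15 = 40%, a failure in the text, not flagged.
- At B = 10% the footnote flags a subject only if burden rises.

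**Step 3. Above B = 50%.** The order reverses. From 60% to 11%, (60 − 11)/60 = 81.7%: a success in the text, yet flagged by the footnote.

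**Step 4. Where subjects are expected.** 0.70 × 36 = 25.2 and 0.70 × 39 = 27.3, so about 25–27 enrolled subjects are expected at B ≤ 20%. There the footnote flags only falls of less than 50%, or less than some smaller figure, against 80% in the text. This assumes that burden just before treatment is distributed much like the screening burden used for stratification.

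**Step 5. How common B > 50% might be.** The plan gives no figure. If the mean of 20% and SD of 13% from the retrospective ablation series in the Introduction are borrowed, the share above 50% among those at 10% or more is 1.3% (normal) to 4.1% (gamma or lognormal). That distribution also puts 47–64% above 20% burden, against the planned 30%, so it does not fit the plan's own expectation. I use it only as an indication that such subjects are few.

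**The case against.** The strongest reply is that this is mostly not a contradiction. Below a burden of 50% the footnote points to a subset of the subjects the text already points to. It does not define failure, does not claim to be the only trigger and forbids nothing. It could be an extra prompt borrowed from the 10% entry criterion. The operative text for the visit and for each arm uses 80% throughout, and much of it is discretionary in any case. A site that follows Sections B and D acts correctly.

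Much of this stands. It limits the consequence but does not remove the inconsistency. Nothing in the plan says the footnote is additional, and as an addition it would be redundant for every subject below 50%, because anyone it flags has already failed. The discretion is also uneven: Section D says a second ablation will be offered, which is firmer than the footnote.

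Three stronger readings are tempting and are not supported:

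- *A countable number of failures will miss re-treatment.* The documents give no distribution of residual burden, no suppression failure rate for the AAD arm, and no indication of how many sites would use Table 2 alone. Not being flagged in Table 2 is not the same as not being re-treated; the number could be zero.
- *The 12-month suppression endpoint is compromised.* Section E and Table 3 define it separately, as a reduction of at least 80%. Its definition does not depend on the footnote.
- *The word absolute in Section D makes success unattainable.* Read as percentage points it would need a starting burden of at least 80%. The visit text, the endpoint definitions and the Protection of Human Subjects section make clear that a relative reduction is meant. This is an editorial slip.

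**Conclusion.** The plan is internally inconsistent, and the Table 2 footnote is wrong as written. The mismatch follows from the wording and the arithmetic alone: the two triggers agree only at a pre-treatment burden of 50% and are furthest apart near the 10% entry threshold. That most subjects fall where the gap is wide rests on the plan's expectation that about 70% will have a burden of 20% or less. Direct opposition is confined to burdens above 50%, which are probably rare.

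The consequence is possible under-identification of failures at sites that work from the table. Its size, and any effect on the rates carried forward to the full trial, cannot be estimated from the documents. The point merits correction because it governs repeat ablation and drug changes and costs almost nothing to put right. It does not call the design or the sample size into question.

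**What to change.** Replace the footnote's residual-burden trigger with failure to achieve a relative reduction of at least 80% from pre-treatment burden, so that Table 2 matches Sections B and D. If the sponsor does want the 10% residual as a further prompt, the footnote should say that it is additional and that the 80% rule governs otherwise.

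Editorial clean-up to make at the same time:
- In Section D, change *absolute* to *relative* in the definition of successful suppression. The same word in Section H, item 3, describes a cited study; check it against that source before changing it.
- Use at least 80% for success in the Treatment – Visit 2 text and in Section F, and below 80% for recurrence in Section E, as Table 3 already does. As written, a fall of exactly 80% counts in Section E as both successful suppression and recurrence.

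The cost is a few words in the footnote and in Sections B, D, E and F, with no new visits, data or subjects.
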